5.0 STUDY THERAPY

5.1 Stereotactic Body Radiotherapy

- SBRT will be administered during the first week of study therapy.
- A single pulmonary or extrapulmonary lesion that measures at least 1 cm in greatest dimension will be treated.
- The target lesion for SBRT will be chosen by the treating radiation oncologist with the following considerations:
 - Confidence that the target lesion is cancerous (based on prior biopsy, growth on serial imaging, and/or hypermetabolic uptake on FDG-PET)
 - Safety of SBRT to the target lesion and ability to meet the dosimetric constraints listed below
- Based on lesion size and location, one of three SBRT schedules will be selected for each patient receiving SBRT to a pulmonary lesion. At least 95% of the planning target volume (PTV) will receive the full prescription dose. Based on the criteria described below, we expect that approximately equal numbers of subjects will receive each of these SBRT schedules:

Schedule	Criteria	Interval between treatments	Course duration
34 Gy x 1	Peripheral tumor measuring \leq 2 cm in greatest dimension and $>$ 1 cm from the chest wall	-	-
18 Gy x 3	Peripheral tumor measuring \leq 5 cm and not eligible for 34 Gy x 1 fraction	42-54 hours	5 days
10 Gy x 5	Central or peripheral tumor not eligible for 34 Gy x 1 fraction or 18 Gy x 3 fractions	18-30 hours	5 days

- Based on lesion location, the following SBRT schedules will be employed for each patient receiving SBRT to an extrapulmonary lesion. At least 95% of the planning target volume (PTV) will receive the full prescription dose. If this cannot be achieved while respecting normal tissue constraints, the prescription dose may be lowered by up to 20%. These treatment schedules are adopted from an ongoing cooperative group clinic trial (NRG-BR001):

Schedule	Target Lesion Location	Interval between treatments	Course duration
10 Gy x 3	Spinal or Paraspinal	42-54 hours	5 days
10 Gy x 3	Osseous	42-54 hours	5 days
10 Gy x 5	Mediastinal or Cervical Lymph Node	18-30 hours	5 days
15 Gy x 3	Liver	42-54 hours	5 days
15 Gy x 3	Abdominal or Pelvic (lymph node or adrenal gland)	42-54 hours	5 days

- The following normal tissue constraints will be used for SBRT planning:

	1 Fraction	3 Fractions	5 Fractions
Brachial plexus	max dose < 17.5 Gy	max dose < 21 Gy	max dose < 30 Gy
Esophagus	max dose < 15.4 Gy	max dose < 30 Gy	max dose < 32.5 Gy
Great vessels	max dose < 37 Gy	max dose < 39 Gy	max dose < 55 Gy
Heart/pericardium	max dose < 22 Gy	max dose < 30 Gy	max dose < 35 Gy
Lungs	At least 1500 cc receiving < 12.5 Gy	At least 1500 cc receiving < 12.5 Gy	At least 1500 cc receiving < 12.5 Gy
Ribs	max dose < 30 Gy	max dose < 30 Gy	max dose < 50 Gy
Skin	max dose < 26 Gy	max dose < 30 Gy	max dose < 40 Gy
Spinal cord	max dose < 14 Gy	max dose < 18 Gy	max dose < 30 Gy
Stomach	max dose < 12.4 Gy	max dose < 27 Gy	max dose < 35 Gy

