2.3 Stereotactic Body Radiotherapy

In recent years, hypofractionated stereotactic body radiotherapy (SBRT) has emerged as an effective treatment option for numerous malignancies. SBRT uses the principles of intracranial stereotactic radiosurgery (large daily doses delivered precisely to a small target volume over a short treatment course) to treat extracranial disease sites. For stage I NSCLC, SBRT has demonstrated excellent local control rates. [18-20] Increased utilization of SBRT has been linked to improvements in overall survival. [21] Serious adverse events following SBRT for NSCLC are very rare[22], except when aggressive SBRT regimens are used to treat central lesions. [23] Importantly, the highly-conformal manner in which SBRT is delivered allows safe treatment of lung tumors in patients with poor pulmonary function.[24] SBRT has also been shown to be safe in extrathoracic disease sites such as the liver and spine.[25, 26]

A wide variety of dosing and fractionation schedules has been used to deliver lung SBRT for NSCLC.[19, 20] Although there is evidence of a dose-response relationship when relatively low-dose regimens (BED < 100 Gy) are used,[19, 20] more intense regimens have yielded consistently excellent results and are considered to be ablative. These include 10-12.5 Gy x 4-5 fractions, 18-20 Gy x 3 fractions, and 25-34 Gy in a single fraction. A randomized RTOG study demonstrated that 34 Gy x 1 fraction is a safe and effective regimen for peripheral tumors.[27] This single fraction dose will be the new standard for the treatment of peripheral lesions in upcoming RTOG SBRT trials. For central lesions, less aggressive regimens such as 10-12 Gy x 5 are recommended. The National Comprehensive Cancer Network (NCCN) now provides guidelines for the selection of an SBRT schedule as well as dosimetric constraints that should be met for each organ at risk and course length:

Table 2. Commonly Used Doses for SABR

Total Dose	# Fractions	Example Indications
25-34 Gy	1	Peripheral, small (<2 cm) tumors, esp. >1 cm from chest wall
45-60 Gy	3	Peripheral tumors and >1 cm from chest wall
48-50 Gy	4	Central or peripheral tumors <4-5 cm, especially <1 cm from chest wall
50-55 Gy	5	Central or peripheral tumors, especially <1 cm from chest wall
60-70 Gy	8-10	Central tumors

Table 3. Maximum Dose Constraints for SABR*

OAR/Regimen	1 Fraction	3 Fractions	4 Fractions	5 Fractions
Spinal Cord	14 Gy	18 Gy (6 Gy/fx)	26 Gy (6.5 Gy/fx)	30 Gy (6 Gy/fx)

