Esophagus	15.4 Gy	30 Gy (10 Gy/fx)	30 Gy (7.5 Gy/fx)	32.5 Gy (6.5 Gy/fx)
Brachial Plexus	17.5 Gy	21 Gy (7 Gy/fx)	27.2 Gy (6.8 Gy/fx)	30 Gy (6 Gy/fx)
Heart/Pericardium	22 Gy	30 Gy (10 Gy/fx)	34 Gy (8.5 Gy/fx)	35 Gy (7 Gy/fx)
Great Vessels	37 Gy	39 Gy (13 Gy/fx)	49 Gy (12.25 Gy/fx)	55 Gy (11 Gy/fx)
Trachea & Proximal Bronchi	20.2 Gy	30 Gy (10 Gy/fx)	34.8 Gy (8.7 Gy/fx)	32.5 Gy (6.5 Gy/fx)
Rib	30 Gy	30 Gy (10 Gy/fx)	30 Gy (7.5 Gy/fx)	32.5 Gy (6.5 Gy/fx)
Skin	26 Gy	30 Gy (10 Gy/fx)	36 Gy (9 Gy/fx)	40 Gy (8 Gy/fx)
Stomach	12.4 Gy	27 Gy (9 Gy/fx)	30 Gy (7.5 Gy/fx)	35 Gy (7 Gy/fx)

*Based on constraints used in recent and ongoing RTOG SABR trials (RTOG 0618, 0813, & 0915).

SBRT is now often used to treat primary tumors and metastases in sites outside the lung, both for NSCLC and for other malignancies. Techniques to safely deliver

SBRT to the skeleton, abdomen, pelvis, and extremities have been established[28]. SBRT for patients with limited metastatic disease may become a standard approach based on recently completed[29, 30] and ongoing randomized trials.

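### The SBRT planning constraints in Section 5.1 set no trachea/proximal bronchi limit, although central lung tumours and mediastinal nodes are treated at 10 Gy x 5

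*Combined protocol and SAP*

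**What the plan says.** Section 5.1 of the combined protocol and SAP assigns 10 Gy x 5 to two groups of targets near the large airways. In the pulmonary schedule table the criterion is "Central or peripheral tumor not eligible for 34 Gy x 1 fraction or 18 Gy x 3 fractions". In the extrapulmonary table the location is "Mediastinal or Cervical Lymph Node".

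The treating radiation oncologist chooses the target lesion. One consideration is confidence that the lesion is cancerous; the other is "Safety of SBRT to the target lesion and ability to meet the dosimetric constraints listed below". The list that follows opens with "The following normal tissue constraints will be used for SBRT planning". It covers brachial plexus, esophagus, great vessels, heart/pericardium, lungs, ribs, skin, spinal cord and stomach. Section 5.2 comes directly after the stomach row.

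Table 3 in Section 2.3 (background) has a row for "Trachea & Proximal Bronchi". The same section says that serious events after SBRT for NSCLC are very rare, "except when aggressive SBRT regimens are used to treat central lesions", and adds: "For central lesions, less aggressive regimens such as 10-12 Gy x 5 are recommended".

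For extrapulmonary lesions only, Section 5.1 lets the prescription fall by up to 20% if coverage and normal tissue limits cannot both be met.

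**The concern.** Section 5.1 makes its own list the planning standard and does not refer back to Table 3. Planning to that list leaves the airway without a numerical cap in the targets where it is most likely to receive a high dose. The protocol itself identifies central lesions as the exception to SBRT's good safety record. It responds with a milder schedule, but that schedule comes with no airway maximum.

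What is at stake is patient safety. Section 7.2 states that this is the first study to combine SBRT with FLT3 ligand and that the full range of toxicities is unknown. The sample size, type I error and power of the PFS4 test do not depend on this point.

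**Working it through.** No figure in the plan needs reproducing. The check compares the two tables and then sets the prescription against the candidate limits.

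**1. Maximum doses in Gy (Table 3 in Section 2.3; constraint table in Section 5.1).**

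| Organ | Table 3: 1 / 3 / 4 / 5 fractions | Section 5.1: 1 / 3 / 5 fractions |
|---|---|---|
| Spinal cord | 14 / 18 / 26 / 30 | 14 / 18 / 30 |
| Esophagus | 15.4 / 30 / 30 / 32.5 | 15.4 / 30 / 32.5 |
| Brachial plexus | 17.5 / 21 / 27.2 / 30 | 17.5 / 21 / 30 |
| Heart/pericardium | 22 / 30 / 34 / 35 | 22 / 30 / 35 |
| Great vessels | 37 / 39 / 49 / 55 | 37 / 39 / 55 |
| Trachea, proximal bronchi | 20.2 / 30 / 34.8 / 32.5 | no row |
| Ribs | 30 / 30 / 30 / 32.5 | 30 / 30 / 50 |
| Skin | 26 / 30 / 36 / 40 | 26 / 30 / 40 |
| Stomach | 12.4 / 27 / 30 / 35 | 12.4 / 27 / 35 |
| Lungs | no row | volume limit |

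**2. Overlap.** Eight organs are shared, at three fractionations: 8 x 3 = 24 limits. Of these, 23 agree; the exception is ribs at 5 fractions (32.5 against 50 Gy). The airway is the only Table 3 organ missing from Section 5.1. No other section sets an airway dose.

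**3. Prescription against the airway value.** 10 Gy x 5 = 50 Gy.
- Against 32.5 Gy: 50 - 32.5 = 17.5 Gy over; 50 / 32.5 = 154%.
- After the full 20% reduction (extrapulmonary only): 50 x 0.8 = 40 Gy; 40 - 32.5 = 7.5 Gy over; 40 / 32.5 = 123%.
- If the correct 5-fraction value were no lower than the 4-fraction 34.8 Gy, then taking 34.8 Gy: 50 - 34.8 = 15.2 Gy over, and 40 - 34.8 = 5.2 Gy over.

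These comparisons apply only to airway tissue receiving the prescription dose. The dose to an airway some distance from the target depends on geometry that the documents do not give.

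**4. Other 5-fraction limits in Section 5.1.** Esophagus (32.5), heart (35) and cord (30 Gy) are well below 50 Gy and will shape central and mediastinal plans. The great-vessel limit (55 Gy) is above the prescription, so it gives little indirect protection. None of them measures airway dose.

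**5. Reliability of the 32.5 Gy figure.** The airway row is the only one of the nine in Table 3 where the limit falls as fractions rise (34.8 Gy in 4, 32.5 Gy in 5). Total and per-fraction figures agree in both cells (4 x 8.7 = 34.8; 5 x 6.5 = 32.5), so a slip in a single digit is not the explanation. The value 32.5 Gy also stands in the esophagus and rib rows. Whether it was mistranscribed cannot be settled from the documents.

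**The case against.** The strongest points on the other side are these.

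- **A row may have been lost.** The Section 5.1 rows are alphabetical, so a trachea row would come last, and the table breaks across the extracted text. This stands as a reason to inspect the source file first. Nothing in the text itself shows a loss.
- **The omission may be deliberate.** Section 5.1 is an edited list: it adds lungs, drops the 4-fraction column and raises one rib limit. A 32.5 Gy cap would also be hard to meet for a target touching the airway. That is possible, but no reason is given. Section 5.1 already accepts the same kind of restriction for the esophagus (32.5 Gy) and heart (35 Gy).
- **Meeting the table is not sufficient.** Safety of treating the lesion is a separate consideration, and Section 7.2 aims to keep severe SBRT complications below 5%. The list is also not exhaustive: it has no liver, kidney or bowel row, although liver and abdominal or pelvic targets are treated. This stands, and it rules out saying that the protocol permits any airway dose. But judgement without a number is weaker than what the protocol requires for nine other organs.
- **Toxicity is monitored.** Section 5.3 ends SBRT for in-field toxicity requiring interruption, Section 6.2 has a six-patient safety pause for Cohort 1, and Section 9.0 provides DSMB review. These act after exposure. A DLT counts only within 30 days and in the first cycle (Section 4.4), so later airway injury would be recorded as an adverse event but not as a DLT.

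A reader might infer that Sections 2.3 and 5.1 contradict each other. They do not: Table 3 is background, and only Section 5.1 states what will be used.

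**Conclusion.** The point holds as an omitted safety limit. One of the nine Table 3 organs is missing from the operative list, and it is the one most relevant to central and mediastinal targets at 10 Gy x 5. The existing safeguards mitigate the gap but do not close it, since none fixes an airway dose.

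The conclusion assumes that the source file has no lost last row. Confidence is therefore moderate.

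The number of patients exposed cannot be estimated. Section 5.1 expects roughly equal use of the three pulmonary schedules, so about a third of pulmonary targets would receive 10 Gy x 5. That third includes peripheral tumours, and neither the central share nor the number of mediastinal targets is given. A reader might infer that patients will be overdosed or have been harmed. The documents support neither: the milder schedule, the safety criterion and the neighbouring-organ limits may keep many plans within Table 3's airway values.

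**What to change.** Check the source file for a lost last row. If there is none, amend the Section 5.1 table with a trachea/proximal bronchi row using the protocol's own Table 3 values: maximum dose < 20.2, < 30 and < 32.5 Gy for 1, 3 and 5 fractions. Before adoption, check the 5-fraction value against the source of Table 3 and correct it in both places if it was mistranscribed. It is the value that governs the 10 Gy x 5 targets.

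No new decision rule is needed. The existing target-selection criterion then covers the airway: if a lesion cannot meet the limit, another is chosen. The 20% reduction should stay confined to extrapulmonary lesions. Extending it to lung lesions is a separate trade-off between dose and eligibility that this point does not require.

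The drafting cost is one table row. The clinical cost is that some central or mediastinal lesions could not be irradiated on study, and a patient with no other SBRT-amenable lesion could not be treated on study. The sample size and the analyses do not change.

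### The five-fraction rib limit in the Section 5.1 planning table (50 Gy) departs without explanation from the protocol's own Table 3 (32.5 Gy), although the other 23 of 24 shared limits agree

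*Combined protocol and SAP*

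**What the plan says.** Section 5.1 introduces its organ limits with the words "The following normal tissue constraints will be used for SBRT planning". In the rib row, the limits for one, three and five fractions are 30, 30 and 50 Gy; the last is printed as "max dose < 50 Gy".

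Section 2.3, part of the background, also tabulates organ limits, in Table 3. The lead-in says that the NCCN provides guidance on schedule selection and "dosimetric constraints that should be met for each organ at risk and course length". The table's footnote gives the source: "Based on constraints used in recent and ongoing RTOG SABR trials". The rib row there reads 30, 30, 30 and 32.5 Gy for one, three, four and five fractions, the last with 6.5 Gy per fraction beside it.

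Five fractions are used in two places in Section 5.1, both as 10 Gy x 5. For lung lesions the criterion is "Central or peripheral tumor not eligible for 34 Gy x 1 fraction or 18 Gy x 3 fractions"; for lesions outside the lung it is "Mediastinal or Cervical Lymph Node". The protocol expects the three lung schedules to be used about equally often.

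**The concern.** The two tables overlap heavily and agree everywhere else, so a single unexplained difference could be a transcription slip in either one. It could also be an intended change whose reason was not written down. A reader cannot tell which.

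The cell has practical effect. Under Section 5.1 the choice of target lesion depends partly on whether the listed constraints can be met. For lesions outside the lung, the prescription may be reduced by up to 20% when target coverage and the normal-tissue limits conflict. The rib limit can therefore bear on which lesion is treated and, outside the lung, at what dose. Section 7.2 also undertakes to plan SBRT so that the expected risk of severe SBRT complications stays below 5%. That undertaking is easier to rely on when each organ limit has a clear origin.

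**Working it through.** No sample-size or power calculation is involved, and the documents give no derivation for either figure. The check is a comparison of the two tables.

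**Step 1: shared cells.** Eight organs appear in both tables, each at one, three and five fractions: 8 x 3 = 24 shared limits. Each entry below is Table 3 / Section 5.1, in Gy.

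| Organ | 1 fraction | 3 fractions | 5 fractions |
|---|---|---|---|
| Spinal cord | 14 / 14 | 18 / 18 | 30 / 30 |
| Esophagus | 15.4 / 15.4 | 30 / 30 | 32.5 / 32.5 |
| Brachial plexus | 17.5 / 17.5 | 21 / 21 | 30 / 30 |
| Heart/pericardium | 22 / 22 | 30 / 30 | 35 / 35 |
| Great vessels | 37 / 37 | 39 / 39 | 55 / 55 |
| Rib | 30 / 30 | 30 / 30 | **32.5 / 50** |
| Skin | 26 / 26 | 30 / 30 | 40 / 40 |
| Stomach | 12.4 / 12.4 | 27 / 27 | 35 / 35 |

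Result: 23 agree and 1 differs.

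Outside this count, the trachea and proximal bronchi row and the four-fraction column are only in Table 3, and the lung row is only in Section 5.1.

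**Step 2: is either figure a reading error?** Table 3 prints a total and a per-fraction dose for each multi-fraction cell. In every one, the total equals the per-fraction dose times the number of fractions; for the rib at five fractions, 6.5 x 5 = 32.5. The Section 5.1 rib row is complete, and its one- and three-fraction entries match Table 3. Both figures therefore appear to be what the protocol prints.

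**Step 3: size of the difference.**
- Difference: 50 - 32.5 = 17.5 Gy.
- Ratio: 50 / 32.5 = 1.54, that is, 54% higher.
- Relative to the five-fraction prescription of 10 x 5 = 50 Gy: the Section 5.1 limit is 50 / 50 = 100% of it, and the Table 3 limit is 32.5 / 50 = 65%.

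**Step 4: who is affected.** Equal use of three lung schedules implies about one third of patients with a lung target on 10 Gy x 5. By the Section 5.1 criteria these are central tumours and peripheral tumours over 5 cm, since 18 Gy x 3 takes other peripheral tumours up to 5 cm. Patients with a mediastinal or cervical node target come on top. The documents do not split the 49 planned patients by target site, and do not say how often a rib would be the limiting organ. No patient count can be derived.

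**Step 5: do the figures identify a slip?** In Table 3, 32.5 Gy is also the five-fraction entry for the esophagus and for the trachea and proximal bronchi. The 50 Gy in Section 5.1 equals the prescription. Either coincidence could suggest a copying error, and neither proves one.

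**The case against.** The strongest reply is that there are not two competing rules. Section 5.1 states which limits are used for planning, and Table 3 is background. The wording that limits should be met describes an outside guideline, not a requirement of this trial. A planner following the protocol has one figure to apply. This stands: the point is an unexplained departure of the operative table from a background table, not doubt about which table governs.

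It can also be said that the departure may be intended. Section 5.1 is not a straight copy: it omits a row and a column of Table 3 and adds a lung row. It also departs from Table 2, which lists three-fraction treatment for peripheral tumours more than 1 cm from the chest wall, whereas the 18 Gy x 3 criterion has no chest-wall condition. This stands too, and is why neither figure is called wrong here. It does not remove the need for an explanation when all the other shared limits were carried over unchanged.

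Three stronger readings are tempting, and the documents do not support them:
- **That 50 Gy is the error and plans are being approved against a wrong limit.** The sources that would settle this are not in the documents.
- **That a limit equal to the prescription hardly restricts a plan.** At least 95% of the planning target volume must receive the full 50 Gy, so a rib within the part receiving full dose would breach a maximum below 50 Gy. The limit still restricts such plans.
- **That the difference alters the dose-limiting toxicity (DLT) count.** Section 4.4 counts grade 3-5 events within 30 days after treatment. Nothing in the documents shows that rib injury would reach that grade in that time, and Section 7.2 does not name ribs among the lung SBRT risks.

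**Conclusion.** The point holds as an unexplained inconsistency in one normal-tissue limit. Section 5.1 allows 17.5 Gy (54%) more to the rib in five fractions than Table 3, and the other 23 shared limits agree. Because Section 5.1 governs, 10 Gy x 5 plans will be checked against 50 Gy.

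The comparison rests only on the two printed tables and needs no outside assumption. It does not show which cell, if either, is a slip, or how many patients are affected. The primary endpoint, the sample size and the analysis are untouched. It should still be settled before further five-fraction planning, because the cell is a patient-safety limit on a schedule in use.

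**What to change.** The rib entries in Sections 2.3 and 5.1 must be reconciled:

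1. The sponsor confirms the intended five-fraction rib limit from its source.
2. An amendment either prints the confirmed figure in both tables or adds a sentence to Section 5.1 saying that the departure from Table 3 is deliberate and why.
3. If the Section 5.1 cell proves to be the slip, five-fraction plans already approved under it are checked against the confirmed figure. If the departure is intended, or the slip is in Table 3, this step is not needed.

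No value is proposed here. The cost is one corrected cell or one sentence by amendment, plus a limited plan check only in the case named in step 3.

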5.2 FLT3 Ligand Therapy (CDX-301)

- Daily subcutaneous injections of CDX-301 (75 µg/kg) will be administered for 5 days, beginning on the first day of SBRT.
- Additional “cycles” of SBRT (to distinct lesions) and CDX-301 may be administered every 2-4 months to subjects who demonstrate evidence of clinical benefit (lack of treatment-related toxicity and no disease progression).
- Study therapy will be discontinued in cases of treatment-related toxicity or disease progression.

5.3 Treatment Modifications

If SBRT is interrupted due to a non-dose-limiting adverse event or any reason other than toxicity, such as a holiday, bad weather, or a transportation problem, the SBRT treatment course will be extended accordingly. In the case of in-field RT toxicities requiring treatment interruption, the SBRT course will be terminated.

CDX-301 therapy will be terminated in the case of any DLT (defined in Section 4.4). CDX-301 will be held if marked leukocytosis (WBCs > 50,000 cells/mm³) is observed.

5.4 Toxicity Management

Excessive Hematopoietic Stimulation

Leukocytosis, especially monocytosis, is expected during administration of CDX-301. Hematological parameters, including WBC and differential, will be monitored as detailed in Section 4.2. CDX-301 will not be administered if marked leukocytosis (WBCs > 50,000 cells/mm³) is observed.

Injection Site Reactions / Dermatological Toxicities

Injection site reactions, generally mild to moderate but occasionally severe, were frequently reported in association with FLT3L administration. Pre-medication with diphenhydramine may be effective in the prevention of pruritic and erythemic reactions and will be considered for subjects who experience local reactions after treatment with CDX-301. Injection site reactions may also be treated with analgesics.

Patients will be monitored by our nursing staff for at least 15 minutes following each CDX-301 injection. Patients may then receive SBRT (based on the selected fractionation schedule, but always on day 1), followed by a physician evaluation that will take place approximately one hour after CDX-301 injection.

